### **Discontinuation Criteria**

Treatment should be permanently discontinued for the following:

- Any Grade 2 drug-related uveitis, eye pain or blurred vision that does not respond to topical therapy and does not improve to Grade 1 severity within the re-treatment period OR requires systemic treatment
- Any Grade 3 non-skin, drug-related adverse event lasting  $>$  7 days with the following exceptions for laboratory abnormalities, diarrhea, colitis, neurologic toxicity, drug-related

uveitis, pneumonitis, bronchospasm, hypersensitivity reactions, infusion reactions, and endocrinopathies:

- Grade 3 drug-related diarrhea, colitis, neurologic toxicity, uveitis, pneumonitis, bronchospasm, hypersensitivity reaction, or infusion reaction of any duration requires discontinuation
- Grade 3 drug-related endocrinopathies, adequately controlled with only physiologic hormone replacement do not require discontinuation. Adrenal insufficiency requires discontinuation regardless of control with hormone replacement.
- Grade 3 drug-related laboratory abnormalities do not require treatment discontinuation except:
  - Grade 3 drug-related thrombocytopenia > 7 days or associated with bleeding requires discontinuation
  - Any drug-related liver function test (LFT) abnormality that meets the following criteria require discontinuation:
    - o Grade  $\geq$  3 drug-related AST, ALT or Total Bilirubin requires discontinuation\*
    - o Concurrent AST or ALT > 3 x ULN and total bilirubin > 2x ULN

\*In most cases of Grade 3 AST or ALT elevation, study drug(s) will be permanently discontinued. If the investigator determines a possible favorable benefit/risk ratio that warrants continuation of study drug(s), a discussion between the investigator and the BMS Medical Monitor/designee must occur.

- Any Grade 4 drug-related adverse event or laboratory abnormality (including but not limited to creatinine, AST, ALT, or Total Bilirubin), except for the following events which do not require discontinuation:
  - Grade 4 neutropenia  $\leq$  7 days
  - Grade 4 lymphopenia or leukopenia or asymptomatic amylase or lipase
  - Isolated Grade 4 electrolyte imbalances/abnormalities that are not associated with clinical sequelae and are corrected with supplementation/appropriate management within 72 hours of their onset
  - Grade 4 drug-related endocrinopathy adverse events, such as, hyper- or hypothyroidism, or glucose intolerance, which resolve or are adequately controlled with physiologic hormone replacement (corticosteroids, thyroid hormones) or glucose-controlling agents, respectively, may not require discontinuation after discussion with and approval from the Principal Investigator
- Any event that leads to delay in dosing lasting > 6 weeks from the previous dose requires discontinuation, with the following exceptions:
  - Dosing delays to allow for prolonged steroid tapers to manage drug-related adverse events are allowed.
  - Dosing delays lasting > 6 weeks from the previous dose that occur for non-drug-related reasons may be allowed if approved by the Principal Investigator.

Prior to re-initiating treatment in a participant with a dosing delay lasting > 6 weeks, the Principal Investigator must be consulted. Tumor assessments should continue as per protocol even if dosing is delayed. Periodic study visits to assess safety and laboratory studies should also continue every 6 weeks or more frequently if clinically indicated during such dosing delays.

- Any adverse event, laboratory abnormality, or intercurrent illness which, in the judgment of the Investigator, presents a substantial clinical risk to the subject with continued nivolumab or ipilimumab dosing

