### **Criteria to Resume Treatment**

Subjects may resume treatment with study drug when the drug-related AE(s) resolve to Grade  $\leq$  1 or baseline value, with the following exceptions:

- Subjects may resume treatment in the presence of Grade 2 fatigue
- Subjects who have not experienced a Grade 3 drug-related skin AE may resume treatment in the presence of Grade 2 skin toxicity
- Subjects with Grade 2 AST, ALT, and/or total bilirubin abnormalities may resume treatment when laboratory values return to baseline and management with corticosteroids, if needed, is complete
- Subjects with combined Grade 2 AST/ALT AND total bilirubin values meeting discontinuation parameters (below) should have treatment permanently discontinued
- Drug-related pulmonary toxicity, diarrhea, or colitis, must have resolved to baseline before treatment is resumed. Subjects with persistent Grade 1 pneumonitis after completion of a steroid taper over at least 1 month may be eligible for retreatment if discussed with the Principal Investigator.
- Drug-related endocrinopathies adequately controlled with only physiologic hormone replacement may resume treatment. Adrenal insufficiency requires discontinuation regardless of control with hormone replacement.

If the criteria to resume treatment is met, scheduling of subsequent will be determined by treating investigator and PI.

Continuing treatment with both ipilimumab and nivolumab is preferred. However, resumption of therapy with just one drug (either nivolumab or ipilimumab) may be considered if 1) the investigator makes the judgement that proceeding with only one drug is necessary to possibly avoid recurrence of an adverse event that would require further dose delay, and 2) it is discussed with the Principal Investigator.

If treatment is delayed  $>$  6 weeks, the subject must be permanently discontinued from study therapy, except as specified in discontinuation section.

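### Section 11 leaves Grade 4 adrenal insufficiency controlled with corticosteroid replacement under two rules with opposite possible outcomes and no stated precedence

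*Combined protocol and SAP*

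**What the plan says.** Four statements in Section 11 of the combined protocol and SAP bear on this event.

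- **Criteria to Resume Treatment.** Endocrinopathies controlled by physiologic replacement alone may resume. The next sentence removes one event from that permission: "Adrenal insufficiency requires discontinuation regardless of control with hormone replacement". No grade is attached.
- **Discontinuation Criteria, Grade 3 endocrinopathy bullet.** The permission and the same carve-out appear together: "Grade 3 drug-related endocrinopathies, adequately controlled with only physiologic hormone replacement do not require discontinuation. Adrenal insufficiency requires discontinuation regardless of control with hormone replacement".
- **Discontinuation Criteria, Grade 4 default.** Permanent discontinuation applies to "Any Grade 4 drug-related adverse event or laboratory abnormality", apart from a list of exceptions.
- **Discontinuation Criteria, Grade 4 endocrinopathy exception.** One exception covers "Grade 4 drug-related endocrinopathy adverse events, such as, hyper- or hypothyroidism, or glucose intolerance, which resolve or are adequately controlled with physiologic hormone replacement" or with glucose-controlling agents. Corticosteroids and thyroid hormones are given in brackets as the replacement hormones: events "adequately controlled with physiologic hormone replacement (corticosteroids, thyroid hormones) or glucose-controlling agents, respectively, may not require discontinuation after discussion". The condition in full is that they "may not require discontinuation after discussion with and approval from the Principal Investigator".

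The Grade 4 exception does not mention adrenal insufficiency and does not refer back to the two places that do.

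**The concern.** The carve-out for adrenal insufficiency was written into two of the three places where Section 11 lets a controlled endocrinopathy continue. It is missing from the third. That third place is also the only one to list corticosteroids as a replacement hormone, which invites a reader to apply it to adrenal insufficiency.

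What is at stake is the handling of a Grade 4 event. An investigator who relies on the resumption criteria would stop both drugs for good. An investigator who relies on the Grade 4 exception could ask the Principal Investigator to approve further dosing. Two patients with the same event could be handled differently, each in apparent compliance with the protocol.

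**Working it through.** No figure in the plan needs to be reproduced, so the check is a comparison of the rules for a drug-related endocrinopathy controlled by replacement.

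| Place in Section 11 | Grade covered | Adrenal insufficiency | Outcome if controlled | Principal Investigator approval |
|---|---|---|---|---|
| Criteria to Resume Treatment, carve-out | None stated | Named | Discontinue | No approval route |
| Discontinuation Criteria, Grade 3 bullet, carve-out | None in the sentence; it sits in a Grade 3 bullet | Named | Discontinue | No approval route |
| Discontinuation Criteria, Grade 3 bullet, other endocrinopathies | 3 | Carved out | No discontinuation required | Not required |
| Discontinuation Criteria, Grade 4 endocrinopathy exception | 4 | Neither named nor excluded | May continue | Discussion and approval required |

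**Step 1. Does Section 11 treat adrenal insufficiency as an endocrinopathy?** Yes. Both earlier places carve it out of a rule about endocrinopathies, which would be unnecessary if it were not one.

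**Step 2. Can the Grade 4 exception reach it?** Read literally, yes. The thyroid disorders and glucose intolerance are introduced as examples, so the list is open. Corticosteroids are not the replacement for either example: thyroid hormone goes with thyroid disease and glucose-controlling agents with glucose intolerance. The word therefore points to some unnamed event. Adrenal insufficiency is the obvious candidate, although the text does not say so.

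**Step 3. Is there a precedence rule?** None is stated. The adrenal insufficiency sentence is the more specific by event, and the Grade 4 exception is the more specific by grade. Appendix 3 cannot settle it, because Section 11 and the appendix both describe its algorithms as guidance that need not be followed.

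**Step 4. What follows for Grade 4 adrenal insufficiency controlled with corticosteroid replacement?**

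- If the adrenal insufficiency sentence covers every grade, treatment stops, and the Grade 4 exception as worded conflicts with it.
- If the Grade 4 exception governs Grade 4 events, treatment may continue with approval, and the resumption sentence, which has no grade limit, conflicts with it.

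Either way, a passage needs editing.

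**Step 5. How often might the event occur?** The only relevant rate is in the Section 3.0 melanoma summary. Among 407 pooled patients on a different dose schedule, 2.0% had drug-related serious adrenal insufficiency of any grade. Suppose that rate carried over to the maximum enrolment of 64, with patients independent:

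- Expected cases: 64 × 0.020 = 1.28, about 1.3.
- Chance of at least one: 1 − 0.98^64 = 0.73.
- Range for assumed rates of 1% and 3%: 1 − 0.99^64 = 0.47 and 1 − 0.97^64 = 0.86.

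These figures describe serious events of any grade, whereas the disputed wording applies only at Grade 4. The same summary lists drug-related Grade 3-4 serious events seen in at least 2% of patients, and adrenal insufficiency is not among them. Its Grade 3-4 serious rate was therefore below that threshold, and the Grade 4 part can be no larger. The documents give no Grade 4 figure.

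**The case against.** The strongest reply is that Section 11, read as a whole, already gives one answer. The Dose Delay Criteria hold both drugs for non-skin drug-related events of Grade 2 or higher, and the thyroid exemption there does not extend to adrenal insufficiency. A Grade 4 adrenal event would therefore be held and would have to satisfy Criteria to Resume Treatment before any further dose. Those criteria require discontinuation with no grade limit. On this view the Grade 4 exception only lifts the automatic Grade 4 stop and overrides nothing. A rule that names the event should also prevail over one that does not. The mention of corticosteroids may be meant for another event, since Section 3.0 lists hypophysitis separately from adrenal insufficiency.

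This reading is plausible and may be what was intended. It does not remove the problem, because the document never says that the resumption criteria prevail over the Grade 4 exception. A reader has to construct that precedence.

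The reply does defeat a stronger reading. A reader might infer that the most severe grade gets the looser rule, so that Grades 1 to 3 must stop while Grade 4 may continue. The text does not settle that:

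- The resumption sentence has no grade limit and can be read as covering Grade 4.
- Continuation at Grade 4 is only permitted, never required, and needs the Principal Investigator's approval.
- For other controlled endocrinopathies, Grade 4 is stricter than Grade 3, because Grade 3 needs no approval.
- A separate bullet requires stopping whenever the investigator judges that further dosing carries substantial clinical risk.

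**Conclusion.** The concern holds as an unresolved conflict between passages of Section 11. Grade 4 adrenal insufficiency controlled with corticosteroid replacement falls literally under two rules with opposite possible outcomes. This rests on reading the example list in the Grade 4 exception as open and on taking corticosteroids to be the replacement for adrenal insufficiency. It does not depend on any event rate.

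Its size cannot be put in numbers. A reader might take the 73% in the working as the chance that the trial meets the disputed wording. It is not: it counts serious events of any grade under another schedule, and the Grade 4 share is unknown and should be smaller.

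A reader might also infer damage to the safety endpoint. Section 14 assesses safety through adverse events, laboratory data and vital signs and names no discontinuation-rate measure, so that effect is not shown. The sample size, error rates and response decision rule in Section 14 are unaffected. The point matters for consistent handling of a severe event, and it is cheap to settle.

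**What to change.** Reconcile the three places in Section 11: Criteria to Resume Treatment, the Grade 3 endocrinopathy bullet and the Grade 4 endocrinopathy exception. Add one sentence stating whether the adrenal insufficiency rule also governs the Grade 4 exception. Then make the mention of corticosteroids in that exception agree with the decision, for instance by saying which events it refers to.

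The sponsor decides which clinical rule applies. This review takes no position on that and does not ask for the same outcome at every grade, only that the passages agree.

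The cost is about one sentence in a protocol amendment, with no added visits, tests or patients.

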### **Treatment of Nivolumab or Ipilimumab Related Infusion Reactions**

Since nivolumab and ipilimumab contain only human immunoglobulin protein sequences, it is unlikely to be immunogenic and induce infusion or hypersensitivity reactions. However, if such a reaction were to occur, it might manifest with fever, chills, rigors, headache, rash, pruritus, arthralgias, hypo- or hypertension, bronchospasm, or other symptoms.

All Grade 3 or 4 infusion reactions should be reported as an SAE if criteria are met. Infusion reactions should be graded according to NCI CTCAE 4.0 guidelines.

Treatment recommendations are provided below and may be modified based on local treatment standards and guidelines as appropriate:

**For Grade 1 symptoms:** (Mild reaction; infusion interruption not indicated; intervention not indicated)

Remain at bedside and monitor subject until recovery from symptoms. The following prophylactic premedications are recommended for future infusions: diphenhydramine 50 mg (or equivalent) and/or paracetamol 325 to 1000 mg (acetaminophen) at least 30 minutes before additional nivolumab administrations.

**For Grade 2 symptoms:** (Moderate reaction requires therapy or infusion interruption but responds promptly to symptomatic treatment [eg, antihistamines, non-steroidal anti inflammatory drugs, narcotics, corticosteroids, bronchodilators, IV fluids]; prophylactic medications indicated for 24 hours).

Stop the nivolumab or ipilimumab infusion, begin an IV infusion of normal saline, and treat the subject with diphenhydramine 50 mg IV (or equivalent) and/or paracetamol 325 to 1000 mg (acetaminophen); remain at bedside and monitor subject until resolution of symptoms. Corticosteroid or bronchodilator therapy may also be administered as appropriate. If the infusion is interrupted, then restart the infusion at 50% of the original infusion rate when symptoms resolve; if no further complications ensue after 30 minutes, the rate may be increased to 100% of the original infusion rate. Monitor subject closely. If symptoms recur then no further nivolumab or ipilimumab will be administered at that visit. Administer diphenhydramine 50 mg IV, and remain at bedside and monitor the subject until resolution of symptoms. The amount of study drug infused must be recorded on the electronic case report form (eCRF). The following prophylactic premedications are recommended for future infusions: diphenhydramine 50 mg (or equivalent) and/or paracetamol 325 to 1000 mg (acetaminophen) should be administered at least 30 minutes before additional nivolumab or ipilimumab administrations. If necessary, corticosteroids (recommended dose: up to 25 mg of IV hydrocortisone or equivalent) may be used.

**For Grade 3 or Grade 4 symptoms:** (Severe reaction, Grade 3: prolonged [ie, not rapidly responsive to symptomatic medication and/or brief interruption of infusion]; recurrence of symptoms following initial improvement; hospitalization indicated for other clinical sequelae [eg, renal impairment, pulmonary infiltrates]). Grade 4: (life threatening; pressor or ventilatory support indicated).

Immediately discontinue infusion of nivolumab or ipilimumab. Begin an IV infusion of normal saline, and treat the subject as follows. Recommend bronchodilators, epinephrine 0.2 to 1 mg of a 1:1,000

solution for subcutaneous administration or 0.1 to 0.25 mg of a 1:10,000 solution injected slowly for IV administration, and/or diphenhydramine 50 mg IV with methylprednisolone 100 mg IV (or equivalent), as needed. Subject should be monitored until the investigator is comfortable that the symptoms will not recur. Nivolumab or ipilimumab will be permanently discontinued. Investigators should follow their institutional guidelines for the treatment of anaphylaxis. Remain at bedside and monitor subject until recovery from symptoms. In the case of late-occurring hypersensitivity symptoms (eg, appearance of a localized or generalized pruritus within 1 week after treatment), symptomatic treatment may be given (eg, oral antihistamine, or corticosteroids).

## **12.0 CRITERIA FOR THERAPEUTIC RESPONSE/OUTCOME ASSESSMENT**

Please refer to Section 10 regarding the timing of tumor measurement assessments.

Response and progression will be evaluated in this study using the new international criteria proposed by the revised Response Evaluation Criteria in Solid Tumors (RECIST) guideline (version 1.1) [Eur J Ca 45:228-247, 2009]. Changes in the largest diameter (uni dimensional measurement) of the tumor lesions and the shortest diameter in the case of malignant lymph nodes are used in the RECIST criteria.

### **12.1 Definitions**

**Evaluable for toxicity.** All patients will be evaluable for toxicity from the time of their first treatment with nivolumab and ipilimumab.

**Evaluable for objective response.** Only those patients who have measurable disease present at baseline and have received at least one dose of therapy will be considered evaluable for response. These patients will have their response classified according to the definitions stated below. (Note: Patients who exhibit objective disease progression prior to the end of cycle 1 will also be considered evaluable.)

**Evaluable Non-Target Disease Response.** Patients who have lesions present at baseline that are evaluable but do not meet the definitions of measurable disease, have received at least one cycle of therapy, and have had their disease re-evaluated will be considered evaluable for non-target disease. The response assessment is based on the presence, absence, or unequivocal progression of the lesions.

### **12.2 Disease Parameters**

**Measurable disease.** Measurable lesions are defined as those that can be accurately measured in at least one dimension (longest diameter to be recorded) as  $\geq 20$  mm by chest x-ray, as  $\geq 10$  mm with CT scan, or  $\geq 10$  mm with calipers by clinical exam. All tumor measurements must be recorded in millimeters (or decimal fractions of centimeters).

Note: Tumor lesions that are situated in a previously irradiated area are not considered measurable unless there has been demonstrated progression in the lesion.

Malignant lymph nodes. To be considered pathologically enlarged and measurable, a lymph node must be  $\geq 15$  mm in short axis when assessed by CT scan (CT scan slice thickness recommended to be no greater than 5 mm). At baseline and in follow-up, only the short axis will be measured and followed.

Non-measurable disease. All other lesions (or sites of disease), including small lesions (longest diameter  $<10$  mm or pathological lymph nodes with  $\geq 10$  to  $<15$  mm short axis), are considered non-measurable disease. Bone lesions, leptomeningeal disease, ascites, pleural/pericardial effusions, lymphangitis cutis/pulmonitis, inflammatory breast disease, and abdominal masses (not followed by CT or MRI), are considered as non-measurable.

Note: Cystic lesions that meet the criteria for radiographically defined simple cysts should not be considered as malignant lesions (neither measurable nor non-measurable) since they are, by definition, simple cysts.

'Cystic lesions' thought to represent cystic metastases can be considered as measurable lesions, if they meet the definition of measurability described above. However, if non-cystic lesions are present in the same patient, these are preferred for selection as target lesions.

Target lesions. All measurable lesions up to a maximum of 2 lesions per organ and 5 lesions in total, representative of all involved organs, should be identified as **target lesions** and recorded and measured at baseline. Target lesions should be selected on the basis of their size (lesions with the longest diameter), be representative of all involved organs, but in addition should be those that lend themselves to reproducible repeated measurements. It may be the case that, on occasion, the largest lesion does not lend itself to reproducible measurement in which circumstance the next largest lesion which can be measured reproducibly should be selected. A sum of the diameters (longest for non-nodal lesions, short axis for nodal lesions) for all target lesions will be calculated and reported as the baseline sum diameters. If lymph nodes are to be included in the sum, then only the short axis is added into the sum. The baseline sum diameters will be used as reference to further characterize any objective tumor regression in the measurable dimension of the disease.

Non-target lesions. All other lesions (or sites of disease) including any measurable lesions over and above the 5 target lesions should be identified as **non-target lesions** and should also be recorded at baseline. Measurements of these lesions are not required, but the presence, absence, or in rare cases unequivocal progression of each should be noted throughout follow-up.

### 12.3 Methods for Evaluation of Measurable Disease

All measurements should be taken and recorded in metric notation using a ruler or calipers. All baseline evaluations should be performed as closely as possible to the

beginning of treatment and never more than 4 weeks before the beginning of the treatment.

The same method of assessment and the same technique should be used to characterize each identified and reported lesion at baseline and during follow-up. Imaging-based evaluation is preferred to evaluation by clinical examination unless the lesion(s) being followed cannot be imaged but are assessable by clinical exam.

Clinical lesions: Clinical lesions will only be considered measurable when they are superficial (e.g., skin nodules and palpable lymph nodes) and  $\geq 10$  mm diameter as assessed using calipers (e.g., skin nodules). In the case of skin lesions, documentation by color photography, including a ruler to estimate the size of the lesion, is recommended.

Chest x-ray: Lesions on chest x-ray are acceptable as measurable lesions when they are clearly defined and surrounded by aerated lung. However, CT is preferable.

Conventional CT and MRI This guideline has defined measurability of lesions on CT scan based on the assumption that CT slice thickness is 5 mm or less. If CT scans have slice thickness greater than 5 mm, the minimum size for a measurable lesion should be twice the slice thickness. MRI is also acceptable in certain situations (e.g. for body scans).

Use of MRI remains a complex issue. MRI has excellent contrast, spatial, and temporal resolution; however, there are many image acquisition variables involved in MRI, which greatly impact image quality, lesion conspicuity, and measurement. Furthermore, the availability of MRI is variable globally. As with CT, if an MRI is performed, the technical specifications of the scanning sequences used should be optimized for the evaluation of the type and site of disease. Furthermore, as with CT, the modality used at follow-up should be the same as was used at baseline and the lesions should be measured/assessed on the same pulse sequence. It is beyond the scope of the RECIST guidelines to prescribe specific MRI pulse sequence parameters for all scanners, body parts, and diseases. Ideally, the same type of scanner should be used and the image acquisition protocol should be followed as closely as possible to prior scans. Body scans should be performed with breath-hold scanning techniques, if possible.

Ultrasound Ultrasound is not useful in assessment of lesion size and should not be used as a method of measurement. Ultrasound examinations cannot be reproduced in their entirety for independent review at a later date and, because they are operator dependent, it cannot be guaranteed that the same technique and measurements will be taken from one assessment to the next. If new lesions are identified by ultrasound in the course of the study, confirmation by CT or MRI is advised. If there is concern about radiation exposure at CT, MRI may be used instead of CT in selected instances.

Endoscopy, Laparoscopy The utilization of these techniques for objective tumor evaluation is not advised. However, such techniques may be useful to confirm complete pathological response when biopsies are obtained or to determine relapse in trials where recurrence following complete response (CR) or surgical resection is an endpoint.

Tumor markers Tumor markers alone cannot be used to assess response. If markers are initially above the upper normal limit, they must normalize for a patient to be considered in complete clinical response. Specific guidelines for both CA-125 response (in recurrent ovarian cancer) and PSA response (in recurrent prostate cancer) have been published [JNCI 96:487-488, 2004; J Clin Oncol 17, 3461-3467, 1999; J Clin Oncol 26:1148-1159, 2008]. In addition, the Gynecologic Cancer Intergroup has developed CA-125 progression criteria which are to be integrated with objective tumor assessment for use in first-line trials in ovarian cancer [JNCI 92:1534-1535, 2000].

Cytology, Histology These techniques can be used to differentiate between partial responses (PR) and complete responses (CR) in rare cases (e.g., residual lesions in tumor types, such as germ cell tumors, where known residual benign tumors can remain).

The cytological confirmation of the neoplastic origin of any effusion that appears or worsens during treatment when the measurable tumor has met criteria for response or stable disease is mandatory to differentiate between response or stable disease (an effusion may be a side effect of the treatment) and progressive disease.

